19.3 Table 2. Summary Table of Patient-reported Outcome Surveys and Time Points

Instruments with Time Frame	# Items	Time (minutes)	Consent T1	Intervention T2	Pre-visit T3	Post-visit T4	Pre-treatment T5
Short Form 12 (SF-12)	12	10	X				
Expanded Prostate Cancer Index Composite (EPIC-26)	26	20	X				
Diet and Lifestyle	10	10	X				X
Patient Demographics (including weight, height, smoking)	6	5	X				
Demographics: Age at diagnosis (calculated from data entry by CRC)	1	1	X				
Control Preferences Scale (CPS)	1	2	X				
Decision Self-Efficacy (DSE)	1	2	X		X		
Choice Predisposition (CP)	2	3	X		X	X	
Access to patient education materials	6	3			X		
Access to Other Diagnostic Tests and External Interventions	6	5			X		
Decision Quality Instrument (DQI)	35	20			X	X	
Risk Reclassification Understanding	1	2			X	X	
Memorial Anxiety Scale for Prostate Cancer (Max PC)	4	5			X	X	
Service Satisfaction with Cancer Care	7	5					X
Total Illness Burden Index for Prostate Cancer – TIBI-CaP	27	10					X
Patient Debrief Telephone Interview (Based on the CIT)	* ³	0-20					X*

³ Qualitative Interview Debrief Interview Guide – See IRB application other study documents for interview guide. Applies only to DSI participant only and not to the usual care participant.

Instruments with Time Frame	# Items	Time (minutes)	Consent T1	Intervention T2	Pre-visit T3	Post-visit T4	Pre-treatment T5
Total Number of Items and Time to Complete Surveys	147	105	58 25		57 31	42 20	40 20-40

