DURATION OF SUBJECT PARTICIPATION AND DURATION OF STUDY	Subjects will be in an active study phase for approximately 4-6 weeks, depending on their scheduling with their local urologist. Within those six weeks, we will approach them about the study; if interested/consented, they will be asked to complete baseline surveys online (paper will be available if preferred); access the decision aid; and talk to the health coach; complete pre-visit surveys; meet with their urologist; and complete follow-up surveys. Once the participant has met with his urologist and made a management decision, he is done with the active intervention phase of the study, and will roll-over into an observational cohort component only of the study. In this phase, we will ask participants to complete surveys on their prostate cancer status and quality of life annually and allow us to access their medical chart to abstract data on their health and prostate cancer status.
CONCOMITANT MEDICATIONS	
Allowed: Participants may take any medications unrelated to their prostate cancer during the study. After their visit with their local urologist when they make a management decision, participants may follow any medical regimen for their prostate cancer.
 
Prohibited: We will not enroll participants who have already received treatment for their prostate cancer.

EFFICACY EVALUATIONS	
PRIMARY ENDPOINT	
 • Knowledge regarding the risks and benefits associated with different management choices for men with localized/early stage prostate cancer.
SECONDARY ENDPOINTS	
 • Anxiety, decision self-efficacy, health-related quality of life. • Choice of prostate cancer management / treatment selection.
OTHER EVALUATIONS	Optional: In the future, we may consider banking saliva and FFPE tumor tissue from already performed biopsies for future research studies. Biospecimen donation will be optional.
SAFETY EVALUATIONS	There are not planned safety evaluations. The active phase of this behavioral intervention is brief, ~4-6 weeks. Participants will not be receiving any active treatment for their cancer during this phase. The main risks may be anxiety or confusion regarding the risks and benefits associated with their current diagnosis and decision ahead, and risk of loss to privacy by participating in a research study.

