5.2 Secondary Efficacy Endpoints

We will assess the impact of our intervention on decision self-efficacy, decision quality, anxiety, and satisfaction, based on participant responses to validated surveys. We will also measure patient understanding of reclassification risk, based on a custom survey designed for this study. (Please see Table 2 for further details on study schedule)

We will measure decision self-efficacy before and after the intervention (before the medical appointment); to assure that the intervention is working as intended. In prior studies we and other researchers have shown that similar pre-consultation decision support interventions are associated with pre/post increases in decision self-efficacy. In the usual care arm, we will measure decision self-efficacy before the medical appointment.

We will measure decision quality, anxiety, and understanding of reclassification risk before and after the medical appointment. The study will record management or treatment approach selected by the participant.

We will measure satisfaction after the medical appointment.

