5.3 Safety Evaluations

There are no anticipated clinical or physical risks associated with participation in this study. The primary anticipated risks associated with this study are losses to privacy, or anxiety or discomfort associated with the survey questions. Participants will be told that their participation is voluntary, and participants will be allowed to skip questions. The key questions that we want participants to answer (or be considered as having missing answers on primary outcomes) are 2 knowledge questions. In our sample size calculations, we will conservatively plan for around 10% missing responses (N~15) on our primary outcome, as well as 10% attrition (N~15 subjects) from consent to visit.

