10.2 Contact 2.1 Obtaining Informed Consent

Includes: enrolling them; administering all baseline/pre-intervention surveys (e.g. SF-12, EPIC, demographics, brief lifestyle questions (e.g., smoking, physical activity), as well as choice predisposition (CP), decision self-efficacy (DSE) and control preferences scale (CPS)) [30, 32, 34, 35]. Site study coordinator alerts patient they must allow time before and after their visit to fill out surveys (on arrival and before leaving the clinic). Note this contact could conceivably be by telephone and the surveys could be filled out by Internet. After all surveys are complete, the site staff will enter the patient into the UCSF system to trigger a call from a student coach.

1. After obtaining the informed consent in REDCaP the CRC will complete the following forms in REDCaP:
 - a. **Subject Identifier Form** in REDCaP and Registration Form in CaPSURE. This action assigns the subject a unique research ID and assignment to study arm (usual care vs, intervention) in REDCaP and CaPSURE secure websites.
 - b. Complete **Study Eligibility Form**.
 - c. Complete **Study Biopsy Form**. Record medical history, including: PSA at diagnosis; tumor stage; prostate volume; biopsy diagnosis date with primary and secondary Gleason grade; and ECOG performance score [36].
2. REDCaP will provide participant with the access to patient reported-surveys and demographics data.
3. If the participant opts for the paper-mode, the CRC will provide the participant with a paper packet of patient surveys.

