10.5 Contact 4 Immediately Upon Arrival at Clinic for Urologist Consultation Visit

Includes: Immediately upon arrival, patient should fill out Time 2 surveys – e.g. on tablet or at a kiosk or on paper. These will include Decision Quality Instrument [38], Max PC [39, 40], DSE [35], Control Preferences Scale [34], Choice Predisposition [35], and Reclassification Risk Understanding. Clinic staff or site study coordinator should print question list and give copies to the patient/family and attending physician for use during the medical visit.

1. Print the QL and PCa SCOPED forms for review by the urologist.

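### Max-PC anxiety is scheduled only at T3 and T4, after the decision support intervention, so the arm comparison cannot be adjusted for a baseline Max-PC score

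*Combined protocol and SAP*

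**What the plan says.** The Protocol Synopsis lists as secondary endpoints "Anxiety, decision self-efficacy, health-related quality of life", and 3.2 and 5.2 also include anxiety. On risk, the Synopsis says "The main risks may be anxiety or confusion regarding the risks and benefits associated with their current diagnosis and decision ahead" and adds loss of privacy; 5.3 names "losses to privacy, or anxiety or discomfort associated with the survey questions".

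The timing is stated consistently:

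- Section 5.2: "We will measure decision quality, anxiety, and understanding of reclassification risk before and after the medical appointment".
- Table 2: the row beginning "Memorial Anxiety Scale for Prostate Cancer (Max PC" (4 items, 5 minutes) is marked at T3 (pre-visit) and T4 (post-visit). T1 is blank.
- Section 10.2, at consent: "administering all baseline/pre-intervention surveys (e.g. SF-12, EPIC, demographics, brief lifestyle questions", followed by choice predisposition, decision self-efficacy and control preferences. Max-PC is not listed.
- Section 10.5, on arrival at the clinic: "These will include Decision Quality Instrument [38], Max PC [39, 40], DSE [35], Control Preferences Scale [34". Section 10.6 repeats Max-PC after the visit. (Both sections call these surveys Time 2; Table 2 calls them T3 and T4.)
- Section 10.3 sets the coaching call 3 days before the visit, so T3 follows the DSI.

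Section 15.4 analyses Max-PC by linear regression, using the approach of 15.3: intervention indicator, site, time, group-by-time interaction, and optional sociodemographic and clinical covariates. No baseline anxiety covariate is named.

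**The concern.** No Max-PC score is taken before the intervention in either arm. The arms can therefore be compared on T3 and T4 levels, but not on change from entry and not with adjustment for entry Max-PC.

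This matters more here than in an individually randomized trial. Under 8.2 and 9.1, site coordinators who know the site's current assignment identify and approach the men. Each site's two arms are made up of different men enrolled in different periods. If the men enrolled in one period are more anxious at entry than those in the other, that difference enters the T3 contrast. Section 15.3 itself allows that randomization by site may not balance the groups. The second loss is precision: the trial is sized for a binary knowledge endpoint, and no power is stated for anxiety.

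**Working it through.** **1. Is the blank T1 cell real?** Sum the Table 2 items.

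- T1: SF-12 12 + EPIC 26 + Diet and Lifestyle 10 + demographics 6 + CPS 1 + DSE 1 + CP 2 = 58, the stated total (the age item calculated from coordinator entry is left out). With Max-PC it would be 62.
- T4: CP 2 + DQI 35 + reclassification risk 1 + Max-PC 4 = 42, the stated total.

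The T1 total has no room for Max-PC and the T4 total includes it, so the blank is not a text-extraction fault.

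**2. The plan's sample size (15.6), to fix the number per arm.** Inputs: 0.50 vs 0.75, power 0.80, intraclass correlation 0.01. Alpha is not stated; two-sided 0.05 is assumed.

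- n per arm = [1.96·√(2·0.625·0.375) + 0.842·√(0.5·0.5 + 0.75·0.25)]² / 0.25² = 57.7, rounded up to 58, so 116 in total. This reproduces the plan.
- Design effect = 1 + (15 − 1)·0.01 = 1.14; 116·1.14 = 132.2; 132.2/8 = 16.5, rounded up to 17 per site-period; 17·8 = 136, or 68 per arm. This also reproduces.

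**3. What a baseline would add.** Let r be the correlation of T1 with follow-up Max-PC. The documents give neither r nor an SD, so r is assumed over a range and differences are in SD units. The design effect of 1.14 belongs to the knowledge endpoint and is borrowed here.

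- Residual variance factor = 1 − r²; equivalent sample-size factor = 1/(1 − r²).
- Standard error without baseline = √(2·1.14/68) = 0.183 SD.
- Minimum detectable difference (two-sided 0.05, power 0.80) = (1.96 + 0.842)·0.183·√(1 − r²).
- Power for an illustrative 0.4 SD difference = Φ(0.4/(0.183·√(1 − r²)) − 1.96).

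| r (assumed) | 1 − r² | Equivalent N factor | Minimum detectable difference | Power at 0.4 SD |
|---|---|---|---|---|
| no baseline | 1 | 1 | 0.51 SD | 59% |
| 0.3 | 0.91 | 1.10 | 0.49 SD | 63% |
| 0.5 | 0.75 | 1.33 | 0.44 SD | 71% |
| 0.7 | 0.51 | 1.96 | 0.37 SD | 86% |

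With a design effect of 1, the first and last minimum detectable differences are 0.48 and 0.34 SD, so the relative gain does not depend on the borrowed value.

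**4. Effect of an entry imbalance.** With equal SDs at T1 and follow-up, an imbalance d at entry carries r·d into the unadjusted contrast. For d = 0.2 SD this is 0.06, 0.10 or 0.14 SD at r = 0.3, 0.5 or 0.7. Chance alone gives an entry imbalance with a standard deviation of about 0.18 SD (the standard error in step 3).

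**5. Current T1 burden.** The Table 2 times for the T1 rows sum to 10 + 20 + 10 + 5 + 1 + 2 + 2 + 3 = 53 minutes, against 25 in the totals row.

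**The case against.** The plan contradicts nothing here: the schedule is the same everywhere, and comparing randomized conditions after the intervention is legitimate without a baseline. A reader might infer that the arms cannot be compared on anxiety at all; that does not follow.

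A reader might also infer that four sites leave the contrast open to lasting differences between sites. The design answers this. Every site contributes men to both arms, and the site and time terms carry over to the secondary models, so stable site differences drop out. Patients are blinded to their site's assignment (8.2), which limits self-selection. What remains is a within-site difference between periods in who is enrolled by staff who know the assignment.

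Nor is that remainder wholly beyond reach. SF-12 is taken at T1, 5.4 lists it among covariates for exploratory analyses, and 15.3 provides for adding unbalanced factors. This stands as a partial remedy. But SF-12 is generic, is not prostate-cancer anxiety, and is not named as a covariate for the anxiety models.

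Two further readings go too far. Calling anxiety the main risk, or Max-PC the trial's harm measure, is not supported: confusion, privacy and survey discomfort are named too, 2.1 says decision support is generally not associated with anxiety, and no safety evaluations are planned. Treating the missing baseline as an inconsistency is weak as well: decision self-efficacy has a T1 value for a stated reason (checking that the intervention works), while decision quality and reclassification understanding have none, like anxiety.

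Finally, the gain depends on r. At 0.3 it is small, and it shrinks further if SF-12 is already in the model.

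**Conclusion.** The point holds as a cheap improvement, not as a flaw that invalidates the anxiety analysis. Without a T1 Max-PC, within-site shifts in entry anxiety between periods can be handled only partly, and precision is given up. On the assumed range of r from 0.3 to 0.7, the loss equals forgoing 1.10 to 1.96 times as many men for this endpoint; r = 0.3 makes it minor and r = 0.7 substantial. These figures rest on 68 evaluable men per arm, the knowledge endpoint's design effect, two-sided 0.05, and no prior adjustment for SF-12. No power target for anxiety is stated, so no planned figure fails. The primary endpoint is unaffected.

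**What to change.** - **Table 2 and 10.2:** add Max-PC to the T1 surveys in both arms. Under 8.4 and 10.2, completing these surveys triggers the coach's contact, so the score would precede the DSI.
- **15.4 and the SAP still to be written:** adjust the T3 and T4 Max-PC linear models for the T1 score, keeping the site and time terms. Do not use T3 as a baseline for T4 when estimating the DSI effect, because T3 follows the DSI.

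Cost: four more items, about 5 minutes by Table 2, taking the listed T1 times from 53 to about 58 minutes. That burden is real, because T1 must be finished before coaching within the roughly two-week window in 10.1, and 5.3 recognizes that survey questions may themselves cause anxiety. Leave Diet and Lifestyle as scheduled: dropping it at T1 to make room is unnecessary and would lose its only value before the DSI.

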19.4 Table 3. Clinician-reported Outcome Measures and Time Points

Instruments with Time Frame for Administration	# Items	Time (minutes)	Consent T1	Intervention T2	Pre-visit T3	Post-visit T4	Pre-treatment T5
Physician Satisfaction	2	5				X	

19.5 Table 4. Interventionist-reported Outcome Measures and Time Points

Instruments with Time Frame for Administration⁴	# Items	Time (minutes)	Consent T1	Intervention T2	Pre-visit T3	Post-visit T4	Pre-treatment T5
Coaching Call Degree of Completion (study-specific; added to uTRAC)	2	2			X		

⁴ Interventionist items are completed by the health coach.

20 APPENDICES

[figure not shown]
20.1 Appendix A. Coaching Intervention – Internet Access to DSI Tool

[Appendix A. Coaching Intervention – Internet Access to DSI Tool](#)

[figure not shown]
PATIENT INSTRUCTIONS FOR DECISION AID – Pioneering Advances in Care and Education

This document summarizes how patients may log in to review educational materials as part of a study. The study asks that patients review the materials prior to a telephone call with a health coach.

Note to patients: If you are not able to log in, you may simply review the contents of the PDF document "Patient-Specific Contents of Decision Aid -Pioneering Advances in Care and Education" that was included in the same email as these instructions. You may note any comments or questions on a piece of paper. If at any time you need assistance, please contact the coach who emailed you this document.

	
Before your coaching session:
 
Go to your unique login page by following the link provided to you by the coach. It will look something like: menlikeme.org/#!/TIA012A000
 
Enter the six-letter Code (password) that the coach also provided for you.
 
Press on the Start button.

--	---

Appendix A. Coaching Intervention – Internet Access to DSI Tool

[figure not shown]
If all goes well, you should now be logged in. You can review the materials by navigating through the tabs from left to right. Click on a tab to see the information for that tab.

Please type any questions or notes you have in the section on the right side of each page. Each tab has its own place for questions and notes. The notes you type on one page, will only appear on that page. At any time, you can click on "Save sidebar notes only as PDF", near the top right of the screen to generate a complete list of all your questions and notes. The PDF file will be called "patient-decision-aid-notes". It will be saved to your computer's usual download location. You may also save a printable copy of the entire presentation, including your notes, by clicking "Save entire presentation plus notes as a PDF". The PDF file will be called "patient-decision-aid-presentation-and-notes".

Click the green "Save" button at the bottom of the screen before moving on to save your questions and notes. Click on the word "hide" if you would like to hide the Notes section. If you would like to view the Notes again, click on the green square that appears when the notes are hidden.

If you need assistance, please contact the coach.

Appendix A. Coaching Intervention – Internet Access to DSI Tool

[figure not shown]
The first tab is called Situation. Please review the summary of your Situation and type any questions or notes in the Notes section on the right side of the screen. If the Notes section is hidden, you can open it up by clicking on the green square near the top right of the screen (circled in red above).

You may follow the links (indicated by blue text) for additional help text. Be aware this will open a new browser window and you may need to return to the current window to continue the presentation.

Click the green "Save" button before moving on to save your questions and notes.

If you need assistance, please contact the coach.

Appendix A. Coaching Intervention – Internet Access to DSI Tool

The second tab is called Choices. Please review the summary of your Choices and type any questions or notes in the Notes section on the right side of the screen.

You may follow the links for additional help text. Be aware this will open a new browser window and you may need to return to the current window to continue the presentation.

Click the green "Save" button before moving on to save your questions and notes.

If you need assistance, please contact the coach.

Appendix A. Coaching Intervention – Internet Access to DSI Tool

[Save sidebar notes only as PDF](#)
[Save entire presentation plus notes as PDF](#)

Clarifying goals and priorities

We aim to help you:

- Live a long life
- Minimize invasive treatments
- Maintain a good quality of life

Below are several health states, or quality of life factors, that could be potentially impacted by therapies for prostate cancer. They are listed in alphabetical order.

For quality of life, drag and drop the items below to order them according to how much they concern you. Put the most important factor at the top and the least important factor at the bottom.

1	Bowel function	Avoiding rectal urgency (felt like you had to pass stool, but did not); bowel movements that cause diarrhea, crampy pain in your abdomen or pelvis
2	Overall mental health	Feeling calm and peaceful; having (a lot of) energy; avoiding feeling downhearted and depressed; avoiding other feelings that may interfere with your social activities
3	Overall physical function	Maintaining moderate activities such as moving a table, pushing a vacuum cleaner, bowling, or playing golf; climbing several flights of stairs; accomplishing the things you would like to do, such as engage in work or other activities; avoiding pain and other physical symptoms that may interfere with social activities
4	Sexual function	Maintaining ability to have an erection; ability to reach orgasm (climax); quality of your erections; frequency of your erections; overall ability to function sexually
5	Urinary function	Avoiding drips, leaks, wetting pants, adult diapers

[figure not shown]
Note: A red arrow points to the number 3 in the list.

The third tab is called Objectives. Please review the Objectives section and rearrange the quality of life items into an order that reflects how much they concern you, with the area of highest concern at the top. If none of them stand out to you, you may leave them in the default order. They are listed in alphabetical order by default.

Also, please type any questions or notes in the Notes section on the right side of the screen. Click the green "Save" button before moving on to save your questions and notes.

If you need assistance, please contact the coach.

Appendix A. Coaching Intervention – Internet Access to DSI Tool

[figure not shown]
The screenshot shows the 'People' tab of the DSI Tool. At the top, there are navigation tabs: Situation, Choices, Objectives, **People**, Evaluation, and Decision. The main heading is 'Clarifying roles and responsibilities in decision making'. Below this, there are two PDF save options: 'Save sidebar notes only as PDF' and 'Save entire presentation plus notes as PDF'. The text explains that before evaluating options, one should designate who on their team (family/friends as well as health care professionals) should have a vote, a voice, or visibility about their decision. A list defines these terms: a **vote** means you want them to make the decision; a **voice** means you want to hear their recommendation and reasoning; and **visibility** means you want to keep them informed. Instructions follow: 'Please list their initials (to protect their privacy) and indicate their role (e.g. spouse, child, urologist, radiation oncologist, etc.)'. A second instruction says: 'Please begin with yourself. Do you see yourself as making the decision (vote), having input (voice), or wanting to just be informed? Then add others, such as your physicians and family members.' At the bottom, there are three boxes for input, each with a title and a sub-instruction: 'Vote' (Make decisions, List initials and roles.), 'Voice' (Input on decisions, List initials and roles.), and 'Visibility' (Keep informed about decisions, List initials and roles.). A red arrow points to the 'Vote' box. On the right side of the screen, there is a green 'Save' button.

The fourth tab is called People. Please review the People section. In the boxes that indicate different level of involvement, list the initials (to protect their privacy) and indicate the role (e.g. – spouse, child, urologist, etc) of anyone who should be involved in treatment decision-making.

Also, please type any questions or notes in the Notes section on the right side of the screen. Click the green “Save” button before moving on to save your questions and notes.

If you need assistance, please contact the coach.

